### 14.3. Additional information

#### 14.3.1. List of BNF and ATC codes used for the identification of strontium ranelate and oral bisphosphonate users.

DRUG NAME	ATC (Aarhus, HS, IPCI, SIDIAP)	BNF (THIN UK)
STRONTIUM RANELATE 2g sachets	M05BX03	06.06.02.00
STRONTIUM RANELATE oral susp granules 2g	M05BX03	06.06.02.00
ALENDRONIC ACID (AS SODIUM SALT) oral soln 70mg/100ml	M05BA04	06.06.02.00
ALENDRONIC ACID (AS SODIUM SALT) tabs 10mg	M05BA04	06.06.02.00
ALENDRONIC ACID (AS SODIUM SALT) tabs 10mg	M05BA04	06.06.02.00
ALENDRONIC ACID (AS SODIUM SALT) tabs 10mg	M05BA04	06.06.02.00
ALENDRONIC ACID (AS SODIUM SALT) tabs 5mg	M05BA04	06.06.02.00
ALENDRONIC ACID (AS SODIUM SALT) tabs 70mg	M05BA04	06.06.02.00
ALENDRONIC ACID (AS SODIUM SALT) tabs 70mg	M05BA04	06.06.02.00
ALENDRONIC ACID (AS SODIUM SALT) tabs 70mg	M05BA04	06.06.02.00
ALENDRONIC ACID (AS SODIUM SALT) tabs 70mg	M05BA04	06.06.02.00
ALENDRONIC ACID (AS SODIUM SALT) tabs 70mg	M05BA04	06.06.02.00
ALENDRONIC ACID (AS SODIUM SALT) tabs 70mg	M05BA04	06.06.02.00
ALENDRONIC ACID 10mg tablets	M05BA04	06.06.02.00
ALENDRONIC ACID 5mg tablets	M05BA04	06.06.02.00
ALENDRONIC ACID 70mg tablets	M05BA04	06.06.02.00
IBANDRONIC ACID 50mg tablets	M05BA06	06.06.02.00
IBANDRONIC ACID conc soln inf 2mg/2ml	M05BA06	06.06.02.00
RISEDRONATE SODIUM 30mg tabs	M05BA07	06.06.02.00
RISEDRONATE SODIUM 35mg tabs	M05BA07	06.06.02.00
RISEDRONATE SODIUM 35mg tabs	M05BA07	06.06.02.00
RISEDRONATE SODIUM 5mg tablets	M05BA07	06.06.02.00
RISEDRONATE SODIUM tabs 30mg	M05BA07	06.06.02.00
RISEDRONATE SODIUM tabs 35mg	M05BA07	06.06.02.00
RISEDRONATE SODIUM tabs 5mg	M05BA07	06.06.02.00

### 14.3.2. List of ICD-10, ICD-9, ICPC and READ codes used for the identification of key health outcomes and covariates.

The sets of codes proposed will be further discussed with each of the academic partners during the first months of the study, and before data extraction.

#### Myocardial infarction / angina pectoris / aorto-coronary bypass surgery

Terms	ICD10 (SIDIAP, Aarhus hospital outpatients)	ICD9CM (HS, Aarhus hospital admissions)	Read Codes (THIN UK)	ICPC (IPCI)
Cardiac infarction	I22 I21			
MI - Myocardial infarction			X200E	
Acute myocardial infarction	I21		G30.. XE0Uh	K75
Acute myocardial infarction, unspecified	I21.9	410.9		
Myocardial infarction (acute) NOS	I21.3	410		
Acute myocardial infarction, unspecified site, episode of care unspecified		410.90		
AMI NOS, unspecified		410.90		
Acute myocardial infarction, subendocardial infarction		410.7	G32..	
Old myocardial infarction*	I25.2	412		
Healed myocardial infarction*			XE2aA G32.11	
Old myocardial infarction*			XE2aA	
Subsequent/recurrent myocardial infarction	I22		G35..	
Subsequent myocardial infarction of unspecified site	I22.9		Gyu36	
Subsequent myocardial infarction of other sites	I22.8		Gyu35 G353.	
Subsequent myocardial infarction of anterior wall	I22.0		G350. GYU3600	
Subsequent myocardial infarction of inferior wall	I22.1		G351.]	
Subsequent acute subendocardial myocardial infarction	I22.2			
Subsequent nontransmural myocardial infarction NOS	I22.2			
Subsequent myocardial infarction (acute) NOS	I22.9			
Reinfarction of myocardium			G35..	
Acute subendocardial myocardial infarction	I21.4		G307.00	
Acute myocardial infarction, subendocardial infarction, episode of care unspecified		410.70		

Terms	ICD10 (SIDIAP, Aarhus hospital outpatients)	ICD9CM (HS, Aarhus hospital admissions)	Read Codes (THIN UK)	ICPC (IPCI)
Nontransmural myocardial infarction	I21.4			
Acute myocardial infarction, of anterolateral wall		410.0	G300.	
Acute anteroseptal myocardial infarction			G3011	
Acute inferior myocardial infarction		410.4	X200K	
Acute myocardial infarction, true posterior wall infarction		410.6		
True posterior myocardial infarction			G306.	
Acute myocardial infarction, of inferoposterior wall		410.3	G303.]	
Other specified anterior myocardial infarction			G301.]	
Acute transmural myocardial infarction of unspecified site	I21.3		Gyu34	
Acute transmural myocardial infarction of anterior wall	I21.0 122.0			
Acute transmural myocardial infarction of inferior wall	I21.1 I21.11 I21.19 122.1			
Acute transmural myocardial infarction of other sites	I21.2 I21.21 I21.29 122.8			
ECG: old myocardial infarction*			3232.	
Anterior myocard.infarct NOS		410.8	G301z	
Other acute myocardial infarct			G30y.	
Other acute myocardial inf.NOS			G30yz	
Inferior myocard. infarct NOS			G308.	
Acute myocardial infarction, of inferolateral wall		410.2	G302.	
Acute lateral myocardial infarction		410.5	X200P	
Lateral myocardial infarct NOS			G305.]	
Acute widespread myocardial infarction			X200S	
Acute posterior myocardial infarction		410.60 410.61 410.62*	X200V	
Posterior myocard.infarct			G304.]	

Terms	ICD10 (SIDIAP, Aarhus hospital outpatients)	ICD9CM (HS, Aarhus hospital admissions)	Read Codes (THIN UK)	ICPC (IPCI)
NOS				
Silent myocardial infarct*			X200a	
ECG: myocardial infarction*			323..	
ECG: myocardial infarct NOS*			323Z.	
Postoperative subendocardial myocardial infarction			XaD2h	
Postoperative myocardial infarction			XaD2b G38..	
Postop MI, unspec			XaD2i	
Acute anterior myocardial infarction		410.1	Xa0YL	
Acute Q wave myocard infarct			XaAC3	
Acute myocardial infarction, subendocardial infarction		410.71 410.72		
Non-Q wave myocardial infarction NOS	I21.4 122.2			
Non-ST elevation (NSTEMI) myocardial infarction	I21.4 122.2			
Unstable angina	I20.0		X2009 G311.13	
Crescendo angina	I20.0		XEOUi G311.11	
Intermediate coronary syndrome	I20.0	411.1		
Angina at rest			X2007 G311.14 G311.200	
Impending infarction			XEOUi G311.12	
Worsening angina			XEOUi	
Other acute forms of ischemic heart disease	I24	411.8		
Preinfarction syndrome			G311.11	
Crescendo angina			G311.12	
Impending infarction			G311.13 G311100	
Unstable angina			G311.14 G311200	
Angina at rest			G311000	
Myocardial infarction aborted			G311011	
Acute coronary syndrome			G311Z00	
Angina decubitus			G330.00	
Nocturnal angina			G330000	
New onset angina			G33Z600	
Old MI / Healed MI *			G32..00 G32.11	

Terms	ICD10 (SIDIAP, Aarhus hospital outpatients)	ICD9CM (HS, Aarhus hospital admissions)	Read Codes (THIN UK)	ICPC (IPCI)
Subsequent MI			G35..	
Other chronic ischaemic heart disease*			G34..	
Presence of aortocoronary bypass surgery*	Z95.1			
Aortocoronary bypass*		36.1		
Coronary artery bypass graft operations*			792..	
PTAC*			793G.	
Other acute and subacute forms of ischemic heart disease (HS data only)**		411		

\* Not to be used for the identification of new (incident) events but just for the characterization of baseline patient characteristics (history of).

\*\* According to partners from HS, all 411\* codes would identify acute myocardial infarction in HS

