### 9.2.5.3. Comparative safety study

Patients with any of the newly defined contra-indications will be excluded:

1. Established, current or past history of ischemic heart disease (IHD),
2. Peripheral arterial disease (PAD),
3. Cerebrovascular disease (CVD),
4. Uncontrolled hypertension, defined by MAH using an operational definition as follows: a patient will be defined as 'uncontrolled hypertension' if the 3 following conditions apply:
  - a. There is a previous diagnosis of hypertension coded in electronic medical records.
  - b. There is documented use of any anti-hypertensive therapy (either at that time or in the previous year before SR/BP initiation).
  - c. There are at least two readings of Systolic Blood Pressure  $\geq 150$  or Diastolic Blood Pressure  $\geq 95$  mmHg recorded in the 3 months prior to SR/BP initiation.

Also, eligible patients with a diagnosis of Paget's disease of bones will be excluded. And for the outcome VTE we will exclude patients with a previous VTE.

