### 9.3.2. Contra-indications and new indications

#### CONTRA-INDICATIONS

- History of Ischemic heart disease (IHD): myocardial infarction, angina pectoris, coronary artery bypass surgery (diagnoses or nitrate use) in year prior to SR therapy initiation.
- History of Peripheral arterial disease (PAD) in year prior to SR therapy initiation.
- History of transient ischemic attack (TIA) or stroke (ischemic or haemorrhagic) in year prior to SR therapy initiation.
- Uncontrolled hypertension, defined by MAH as the combination of the following: 1.previous diagnosis of hypertension coded in electronic medical records; 2.documented use of any anti-hypertensive therapy (either at that time or in the previous year before SR therapy initiation); and 3. at least two readings of Systolic Blood Pressure  $\geq 150$  or Diastolic Blood Pressure  $\geq 95$  mmHg recorded in the 3 months prior to SR therapy initiation.
- History of thromboembolic events (pulmonary embolism and deep venous thrombosis) in year prior to SR therapy initiation.

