**Table (9.4) 1 - Overview of contributing databases**

Country	Netherlands	United Kingdom	Denmark	Italy	Spain
Name of the database	IPCI	THIN	Aarhus	HSD- Thales	SIDIAP
Type of database	MR	MR	ADM	MR	MR
# patients, millions	1.2	3.5	1.8	1.5	5.1
Age categories	All	All	All	>15 years	>15 years
Date in	Yes	Yes	Yes	Yes	Yes
Date out	Yes	Yes	Yes	Yes	Yes
Date death	Yes	Yes	Yes	Yes	Yes
Prescriptions					
Outpatient Rx	Yes (specialist incomplete)	Yes (specialist incomplete)	Yes	Yes (specialist incomplete)	Yes (specialist incomplete)
Coding of drugs	ATC	BNF/Multilex	ATC	ATC	ATC
Dosing regimen	Yes	Yes	No	Yes (incomplete)	Yes
Outcomes					
Hospitalizations	Yes	Yes	Yes	Yes	Yes
Outpatient diagnoses	Yes	Yes	Yes	Yes	Yes
Coding of disease	ICPC	READ	ICD-10	ICD-9 CM	ICD-10
Cause of death	Yes (from text)	If linked to death registry	Yes	No	No

*ADM = administrative; ATC = Anatomical Therapeutic Chemical; BNF = British National Formulary; ICPC = International Classification of Primary Care; MR = Medical Records*

All of the chosen databases comply with European Union (EU) guidelines on the use of medical data for medical research and have been validated for pharmaco-epidemiological research (Cazzola, 2011; Vlug, 1999).

The databases will be THIN (UK), HSD (Italy), IPCI (NL), the Aarhus University Database (DK) and SIDIAP (Spain). Table (9.4) 1 provides an overview of key elements of these databases. The total number of persons in the source population will be around 12 million as of 2012.

HSD (Italy), IPCI (Netherlands), SIDIAP (Spain) and THIN (UK) are listed under the ENCePP resources database: ([www.encepp.eu/encepp/resourcesDatabase.jsp](http://www.encepp.eu/encepp/resourcesDatabase.jsp)).

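### Ischaemic heart disease is defined three different ways, and the code table lists chronic IHD and angioplasty for THIN only and plain stable angina for no database

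*Protocol*

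**What the plan says.** Protocol section 9.2.5.3 states that "Patients with any of the newly defined contra-indications will be excluded" and lists first "Established, current or past history of ischemic heart disease (IHD", with no limit by subtype or time.

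Section 9.3.2 describes the same contraindication as "myocardial infarction, angina pectoris, coronary artery bypass surgery (diagnoses or nitrate use) in year prior to SR therapy initiation".

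The Appendix 14.3.2 table for infarction, angina and bypass supplies the codes. Its row "Other chronic ischaemic heart disease" has a Read code (G34..) and nothing under ICD-10, ICD-9-CM or ICPC. The angioplasty row is likewise Read only (793G.). By contrast, "Old myocardial infarction" has ICD-10 I25.2 and ICD-9-CM 412.

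The table heads its ICD-9-CM column "ICD9CM (HS, Aarhus hospital admissions"), while Table (9.4) 1 gives, in the order Netherlands, UK, Denmark, Italy, Spain: "Coding of disease ICPC READ ICD-10 ICD-9 CM ICD-10". On that row Denmark (Aarhus) uses ICD-10.

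**The concern.** Section 9.9 puts restriction to patients without contraindications first among its methods against between-person confounding. That works only if the contraindication can be found in each database. Section 9.6.6 treats absence of a record as absence of the condition, so a patient whose IHD has no listed code counts as IHD-free. Section 9.3.4 lists neither IHD nor nitrate use as a covariate, so adjustment cannot fully recover what restriction misses.

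Three outputs are exposed:
- the comparison of SR with bisphosphonates (BP), through residual IHD in the cohort;
- the incidence rates by number of contraindications (9.7.3.2), through patients placed in too low a stratum;
- the IHD prevalence in the risk-minimisation study, which would differ between countries partly because the code lists differ.

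The Aarhus contradiction is a separate matter. Section 9.3.1 finds the safety endpoints there in the hospital discharge and death registry, without manual validation. The choice of column therefore governs myocardial infarction (MI) case finding as well as IHD history.

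**Working it through.** **1. The definitions side by side**

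| Item | 9.2.5.3 | 9.3.2 | ICD-10 | ICD-9-CM | Read (THIN) | ICPC (IPCI) |
|---|---|---|---|---|---|---|
| Acute MI | yes | yes | yes | yes | yes | K75 |
| Old MI | yes | only if in the prior year | I25.2 | 412 | yes | none |
| Unstable or similar angina | yes | yes | I20.0 | 411.1 | several rows | none |
| Plain stable angina | yes | yes (angina) | no row | no row | no row | none |
| Other chronic IHD | yes | not named | none | none | G34.. | none |
| Bypass surgery | yes (as IHD) | yes | Z95.1 | 36.1 | 792.. | none |
| Angioplasty | yes (as IHD) | not named | none | none | 793G. | none |
| Nitrate use | not named | yes | no code listed for any database | | | |

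The Read angina rows cover unstable, crescendo, worsening, at rest, decubitus, nocturnal and new-onset forms. None is plain stable angina. The angina of 9.3.2 is therefore not fully coded anywhere.

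Two further mismatches follow. Section 9.3.2 uses a one-year look-back, against past history without limit in 9.2.5.3. It is also tied to the start of SR and gives no equivalent for BP starters; 9.2.5.3 names both drugs only for hypertension.

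**2. Share of SR users in databases without the chronic IHD and angioplasty codes**

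Inputs from Table (9.5) 1, incident users in 2012: HSD 1,209; SIDIAP 4,008; THIN 514; Aarhus 46; IPCI 42; total 5,819.

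- Outside THIN: 5,819 − 514 = 5,305, and 5,305 / 5,819 = 91.2%.
- SIDIAP 68.9%, HSD 20.8%, Aarhus 0.8%, IPCI 0.7%; THIN 8.8%.

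This is the share of users in affected databases, not the share of patients misclassified.

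**3. The plan's figure that depends on the exclusion**

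Section 9.5.2 expects at least 25,128 SR users after exclusion.

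- Excluded share: 0.90 × 0.192 + 0.10 × 0.295 = 0.2023.
- 31,500 × (1 − 0.2023) = 25,127.55, so 25,128 reproduces.

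The figure uses a published prevalence, not the code lists, and is not wrong because of this point.

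**4. Illustration of retained patients**

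The missed share is an assumption. Excludable patients outside THIN: 31,500 × 0.2023 × 0.9117 ≈ 5,810.

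- 5% missed: 290 stay in, 1.1% of the retained SR cohort.
- 10% missed: 581, or 2.3%.
- 25% missed: 1,452, or 5.5%.
- 50% missed: 2,905, or 10.4%.

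The prevalence used combines cardiac, cerebrovascular and peripheral arterial disease, so these overstate a loss from IHD alone.

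**5. Illustration of bias, for starters from June 2013 only**

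Factor on the odds ratio = (1 + u_SR(RR − 1)) / (1 + u_BP(RR − 1)), where u is the undetected IHD prevalence in each group and RR its MI rate ratio. All inputs are assumed: u_BP 2% to 8%, u_SR from 0 to a quarter of u_BP, RR 3 to 4.

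- Strongest: 1 / (1 + 0.08 × 3) = 0.806; a true 1.5 reads 1.21.
- Weakest: (1 + 0.005 × 2) / (1 + 0.02 × 2) = 0.971; a true 1.5 reads 1.46.

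Section 9.5.2 expects 500 to 1,000 SR starters a year in 2013–2015, that is 1,500 to 3,000 of 31,500 to 33,000 (5% to 9%). With its own rate and follow-up, and the retained share from step 3, MI cases among them number about 1,500 × 0.7977 × 2 × 0.0019 = 4.5 to 3,000 × 0.7977 × 2 × 0.0019 = 9.1. Random error would swamp a factor of 0.81 to 0.97.

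**The case against.** **The code lists are provisional.** Section 9.6 and Appendix 14.3.2 call them proposals to be discussed with partners before extraction, and 9.6.4 benchmarks rates and investigates outliers. This makes correction cheap. But sections 9.2.5.3 and 9.3.2 are not provisional, and nothing commits the partners to closing these particular gaps.

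**Section 9.2.5.3 may be only the label, with 9.3.2 as its operational definition.** That is a natural reading, and it would bring nitrate use into the exclusion. It leaves the look-back conflict, the wording for SR alone, the missing nitrate code and the incomplete coding of angina.

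**Nitrate use and free text recover some patients.** This stands. Those retained are only patients with no listed code, no nitrate use and no free-text hit. Free-text search (9.6.1) applies only where free text exists, and the protocol does not say that SIDIAP, the largest contributor, has it. Old MI and bypass are coded in both ICD systems, so it would be wrong to infer that all chronic coronary disease is lost outside THIN. It would be equally wrong to infer that THIN is complete, since stable angina is missing there too.

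**Adjustment helps.** Lipid-lowering drugs, antiplatelets, beta-blockers and calcium channel blockers are candidate confounders. They are partial proxies, kept only on a 10% change in the estimate (9.9).

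**In the time series each database is its own control** (9.7.2.2), and 9.9 already admits underestimation of contraindications. Stable under-capture does not create a false trend. It does lower the level, and if a constant fraction is captured, an absolute change shrinks by the same fraction. Comparisons between countries stay affected.

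**Conclusion.** The inconsistency is on the page and should be corrected before extraction. The three definitions differ in subtype, look-back and drug group. The chronic IHD and angioplasty rows are uncoded in databases with 91.2% of 2012 incident SR users. Some IHD patients would therefore remain in a cohort described as free of contraindications, and measured IHD prevalence would vary with the coding system. How many cannot be derived from the protocol, and no stated sample size or power figure is wrong because of it.

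A reader might infer that the SR odds ratio will be biased from 1.5 to 1.21–1.46. The documents do not support that as a finding: every input is assumed, and allowance for nitrate capture or adjustment is absent. A shift toward or below 1 is plausible only from June 2013, when 9.2.2 says patients with the new contraindications should no longer receive SR while BP prescribing has no such limit in the protocol. The protocol fixes no direction for the earlier period, and the later stratum is small. The range is at most an illustration for that stratum.

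A reader might also infer that Aarhus admissions will be searched with codes that do not exist there, losing its MI cases (570 × 1.8 / 13.1 = 78 if BP use follows population). The documents show a contradiction, not which entry is right, and do not give the share of cases found through admissions. It concerns MI, unstable angina and bypass history in a source with 0.8% of 2012 incident SR users. It does not affect the chronic IHD or angioplasty rows, which are empty in both ICD columns.

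**What to change.** Before extraction:

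1. State one IHD definition, with one look-back, and use it in both 9.2.5.3 and 9.3.2. Apply it identically to SR and BP starters, and include the nitrate proxy with its ATC and BNF codes.
2. Add history-only codes for stable angina to all four columns of the 14.3.2 table. Copying the Read column's coverage would not achieve this.
3. Add history-only codes for chronic IHD and coronary revascularisation to the ICD-10, ICD-9-CM and ICPC columns where a code exists, and free-text terms where none does.
4. Confirm with the Aarhus data custodian which coding system its admissions use, reconcile the 14.3.2 header with Table (9.4) 1, and search admissions with that system.

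The cost is an edit to two definitions, one code table and one header, plus a query to one custodian. The eligible cohort for the comparative study becomes slightly smaller.

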### 9.3. Variables

#### 9.3.1. Safety endpoints

**Ascertainment of cases:** cases will be all persons with a first occurrence after cohort entry of:

- Acute myocardial infarction.
- Thromboembolic events (deep venous thrombosis and pulmonary embolism).
- Cardiovascular death.

Cases will be identified from the medical records (see codes in Appendix 14.3).

Acute myocardial infarction has been recently validated in all of the participating data sources (Coloma, 2013; Ramos, 2012) and will therefore not need further linkage or validation studies.

Thromboembolic events have been validated in the UK CPRD/THIN (Lawrenson, 2000) and Aarhus (Severinsen, 2010), and these previously validated algorithms will be used to identify cases. A random sample of cases of thromboembolic events in each data source will be validated using either free text manual review (IPCI, HSD, and Aarhus) or linkage to hospital admissions data (THIN and SIDIAP). If the estimated positive predictive value in these samples is >75%, no further validation will be performed for thromboembolic events. Otherwise, all the events observed in the safety study (i.e. cases) will be individually validated, and only those found to be valid (either by manual review or related hospital admission from hospital records databases, as proposed above) will be defined as cases.

As for cardiovascular death, HSD, IPCI and SIDIAP will combine ICPC and ICD9/ICD10 codes (for hospital admission/primary care records) respectively with mortality using a time specific window to define cardiovascular death. In THIN, data will be linked to the official mortality registry (office for national statistics) for cause of death. In Aarhus, safety endpoints will be identified in the patient registry (hospital discharge and death registry) and no manual validation in the medical records will be done.

**Control selection:** In the nested case control study, each case will be matched by age (same year of birth), index date, gender, and country/data source to 10 controls selected from the cohort using incidence density sampling.

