## Pulmonary / deep vein thrombosis

Term/Description	ICD10	ICD9CM	Read codes	ICPC
Phlebitis and thrombophlebitis of femoral vein	I80.1			
Phlebitis and thrombophlebitis of other deep vessels of lower extremities	I80.2			K94.01 K94.15
Pulmonary embolism	I26			K93
Phlebitis and thrombophlebitis of deep vessels of lower extremities		451.1, 451.2**		
Acute venous embolism and thrombosis of deep vessels of lower extremity		453.4		
Pulmonary embolism and infarction		415.1		
Pulmonary embolism Pulmonary embolus Post operative pulmonary embolus Recurrent pulmonary embolism * Deep vein phlebitis and thrombophlebitis of the leg Deep vein thrombosis Deep vein thrombosis, leg DVT - Deep vein thrombosis Thrombophlebitis of the femoral vein Thrombophlebitis of the popliteal vein Thrombophlebitis of the anterior tibial vein Thrombophlebitis of the posterior tibial vein Deep vein thrombophlebitis of the leg unspecified Deep vein thrombosis of leg related to air travel Deep vein thrombosis of lower limb Deep vein thrombosis of leg related to intravenous drug use Deep vein thrombosis of peroneal vein Deep vein phlebitis and thrombophlebitis of the leg NOS Thrombosis of vein of leg  Post operative deep vein thrombosis [V] Personal history deep vein thrombosis * [V] Personal history DVT- deep vein thrombosis * [V] Personal history of pulmonary embolism * Thromboembolic pulmonary hypertension *			G401.00 G401.12 G401000  G401100 G801.00  G801.11 G801.12 G801.13 G801600  G801700  G801800  G801A00  G801B00  G801C00  G801D00  G801E00  G801F00  G801z00   G802000  SP12200  ZV12800	

			ZV12811 ZV12900 G41y100	
Personal history of pulmonary embolism		V12.55		
Personal history of venous thrombosis and embolism		V12.51		
Iliac vein thrombosis/embolism			G08Y	

*\* Not to be used for the identification of new (incident) events but just for the characterization of baseline patient characteristics (history of).*

*\*\* Code to be used for HSD data only following suggestion from co-investigators.*

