## Osteoporotic fracture

Fracture site	ICD10	ICD9CM	READ	ICPC
			XA0FK, XaB0o, XE1pj, S3zz., TC7..	L76
Unspecific	M80		N3303, N3315, N3316, N331B, NyuB0, NyuB8	
Clavicle	S42.0	810	S20..., S20z.	
Scapula	S42.1	811	S21..., S21z.	
Humerus	S42.2, S42.3, S42.4	812	S22..., S22z., XA0GS, XA0GT, XA0GQ	
Radius/Ulna	S52	813	S230., S2317, S2318, S2319, S2323, S234C, S234D, S234E, S2333, S2356, S235C, S235D, S235E, S23x., S23y., S23z., XE1ks, XA0GX, XA0Ga, XA0Gb, XA0Gl, XA0GV, XA0GW, XA85j, XM16p, XE1ee, XE1kw, XE1kv, XE1ky, XE1kz, 7K1LL	L72
Carpal bone/s	S62.0, S62.1	814	S24..., S4C0y, S4C1y, S4C2y, S4C3y, XA0E4, XA0ES	
Metacarpal bone/s	S62.2, S62.3, S62.4	815	S25..., Xa3he, XA0Gq, XA0Gr	
Arm/upper limb (unspecific)		818		
Hand (unspecific)				L74
Spine	S12, S22.0, S22.1, S32.0, S32.7, S32.8, T08	805	S10z., XE1kW, XE1pT, S10B., XA0G8, Syu34, XA0GB, XA0GM, XA0GN, XE0ln, 7J42z, 7J41., 7J43y, 7J43z, XE0lo, XA0Ds, XA0Dt, XA0Dv, XA0Dw, S10x., S10y., XE1kX, S10A2, XM1JV, XE1kf, Xa1u3, S114., S115., 7J420, 7J42y, 7J421, 7J423, 7J424, 7J425, XE1kn, S11z., XM1JU, N3318, N3319, N331A	
Rib/s/Sternum	S22.2, S22.3, S22.4, S22.5	807.0 to 807.4	XA0Gv, XA0Gw, XA0Gy, XA0Gz, S120., S121., S122., S123., S4J00, S4J10, S4J20, S4J30	
Pelvis	S32.1 to S32.5, S32.8	808	XA0H0, Xa3hd, S10B., S13., Syu34, S4J01, S4J11, S4J21, S4J31, S108., S109.	

Hip/Proximal femur	S72.0, S72.1		820	XaBDT, XaBDU, XaEJD, XA0HE, XA0HF,XA0HG, XA0HH, XA0HI, XA0HK, XA0HL, XE114, XE115, XE116, XE117, XE118, XE119, XM1Ne, XM1Nf, XM1Ng, XM1Nh, XM1Ni, XM1Nj, 7K1L4, X601I, X601L, X601M, X601N, X601P, X601S, X601T, X601U, XaEJD, S30w., S30x., S30z., S300., S301., S302., S303., S3003, S3004, S3014, S304.	L75
Femur (others/unspecific)	S72.2 to S72.9		821	XA0HC, XA0HD, XA0HJ, XA0HN, XA0HO, XA0HP, XA0HQ, XA0HR, XE11A, XE2ru, XE2rv, S31., S31z., S3101, S3111, S312x, S312z, S3120, S3122, S3132, S313z, S3130, 7K1L5	L75
Patella	S82.0		822	S32z., S32., XaCln	
Tibia/Fibula	S82.1 to S82.4		823	S33z., S33., Xa0m8, Xa85k, XA0HT, XA0HU, XE11B, XE11C, XE11D, XM00Y, XM16s, 7K1L7	L73
Ankle	S82.5, S82.6, S82.8		824	S34., S4G1., 7K1L8, 7K1E4, XA0Ee, XA0EG, XA0Hh, S4G., Xa1n1, Xa1mv, Xa1mz	
Tarsal/metatarsal bone/s	S92.0 to S92.3		825	Syu94, XA0Hi, XE11H, S353., XE11F, S35z., S3520, S3530, S352z, S353z	
Foot (unspecific)					L74

*Not considered as osteoporotic fractures: skull, face, jaw, coccyx, phalanx (fingers and toes), ankle and cervical spine*

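### The Appendix 14.3 code lists contradict their own labels, footnotes and definitions in five places and should be corrected before data extraction

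*Protocol*

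**What the plan says.** - **Case definition.** Section 9.3.1 names three safety endpoints: AMI, thromboembolic events and cardiovascular death. It says that "cases will be all persons with a first occurrence after cohort entry of" one of these, and "Cases will be identified from the medical records (see codes in Appendix 14.3"). AMI is said to need no further validation. For thromboembolic events a random sample is validated in each source, and all cases are validated only if the positive predictive value (PPV) is not above 75%.
- **AMI codes.** The first table of 14.3.2 covers infarction, angina and bypass surgery together. Its footnote says of starred codes: "Not to be used for the identification of new (incident) events but just for the characterization of baseline patient characteristics (history of"). A second footnote reports that all 411 codes identify AMI in HSD.
- **Old infarction.** The row "Acute myocardial infarction, subendocardial infarction" carries ICD-9-CM 410.7 and Read G32.., unstarred. The row "Old MI / Healed MI" is starred and carries G32..00 and G32.11.
- **Thromboembolism.** The row "Personal history of venous thrombosis and embolism" (V12.51) and the matching pulmonary embolism row (V12.55) are unstarred.
- **Comparator.** The list in 14.3.1, titled for strontium ranelate (SR) and oral bisphosphonate users, includes "IBANDRONIC ACID conc soln inf 2mg/2ml".
- **Fracture.** The osteoporotic fracture table has an Ankle row, and its footnote reads: "Not considered as osteoporotic fractures: skull, face, jaw, coccyx, phalanx (fingers and toes), ankle and cervical spine".
- **Status.** Sections 9.6 and 14.3.2 describe the lists as proposals, to be discussed with the academic partners before extraction.

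**The concern.** The same table serves two purposes: the ischaemic heart disease contraindication, where angina belongs, and the AMI endpoint, where it does not. A programmer who treats every unstarred code as an event code would count angina as AMI. The other slips similarly let an old infarction or a recorded history of thrombosis count as a new event. Such cases are probably little related to current exposure. In a safety study they push the comparison towards no difference, which is the falsely reassuring direction, and they raise the absolute rates. The validation waiver for AMI rests on validation of AMI and says nothing about angina codes. The infusion product blurs the comparator. The fracture contradiction reaches the severe-osteoporosis measure, which section 9.7.2.2 lists among the primary outcomes for the risk minimisation measures (RMM).

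**Working it through.** No planned figure has to be reproduced; the check sets tables against their footnotes and against the body text.

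1. **Angina and other acute ischaemic heart disease.** Unstarred rows include unstable, crescendo, rest, worsening, decubitus, nocturnal and new-onset angina (I20.0, 411.1, the G311 group, G330.00, G330000, G33Z600) and other acute forms of ischaemic heart disease (I24, 411.8). Old infarction, silent infarction, chronic ischaemic disease and bypass are starred, so the mark was applied row by row. Section 9.3.2 lists angina under the contraindication; section 9.3.1 does not list it as an endpoint. Only HSD has an explicit rule (411 codes are AMI). The 411.1 and 411.8 rows stand in a column headed for HSD and Aarhus admissions, and I20.0 and I24 in the column for SIDIAP and Aarhus outpatients; no reason is given there. As the table reads, the IPCI column holds only K75.

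2. **Read G32...** The appendix elsewhere treats a trailing 00 as the same concept: G663. and G663.00 are both brain stem stroke syndrome. So one code is acute and unstarred in one row, old and starred in another. Acute subendocardial infarction has its own Read code in the table, G307.00, so marking G32.. history-only need not lose those events. The other old-infarction codes (I25.2, 412, XE2aA, G32.11, 3232.) are starred.

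3. **V12.51 and V12.55.** Both are labelled personal history. The stroke table stars V12.54, and the Read personal-history entries in the thromboembolism table are starred. Only these two ICD-9-CM codes break the pattern.

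4. **Infusion product.** Section 9.3.3 defines the oral comparator by ATC code, with M05BA06 for ibandronate. The infusion concentrate has that same code, so ATC alone cannot remove it. Product-level data can help in places: section 9.4.4 says the Aarhus package identifier gives route of administration.

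5. **Fracture.** The table includes ankle (S82.5, S82.6, S82.8; 824; Read codes), its footnote excludes ankle, and section 9.3.4 excludes only skull/face, fingers and toes. The footnote also excludes cervical spine, but the Spine row is not divided by region. Section 9.3.4 refers the reader to 14.3.1, which is the drug list.

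6. **Direction of effect.** Let a share f of counted AMI cases be non-AMI with no link to SR (an assumption). Section 9.5.2 uses 20% exposure in controls and an odds ratio of 1.5. Exposure in true cases is then 1.5 × 0.20 / (0.80 + 1.5 × 0.20) = 0.30 / 1.10 = 0.273. Exposure in counted cases is (1 − f) × 0.273 + f × 0.20. For any f between 0 and 1 this lies between 0.20 and 0.273, so the expected odds ratio lies between 1 and 1.5. The documents give no value or range for f.

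**The case against.** The footnote bars starred codes from incident use; it does not say that every unstarred code is an endpoint code. The same asterisk and footnote appear in the stroke/TIA and peripheral vascular tables, and neither condition is a safety endpoint. The HSD note on 411 codes would be needless if all unstarred codes already meant AMI. A reader might infer that angina counts as AMI in every database; outside HSD the documents do not say so. What stands is narrower: no mark or separate list shows which unstarred codes form the AMI endpoint.

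A reader might also infer that old-infarction codes in general are treated as events. Only Read G32.. is, and only in THIN. The comparative study excludes patients with past ischaemic heart disease (9.2.5.3). That protection is incomplete: section 9.3.2 looks back only one year for this history, and the incidence-rate analysis has no exclusions (9.2.5.2).

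For thromboembolism, the comparative study excludes patients with a previous event, and a sample of cases is validated. Both help. But a PPV above 75% ends validation with the history codes still in, and the exclusion does not apply to the incidence rates.

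The lists are provisional, and section 9.6.4 plans benchmarking of incidence rates. This lowers the severity. It does not settle the contradictions, because section 9.3.1 points to these lists.

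Finally, a reader might put a number on lost power. That needs a contamination share the documents do not give. It also depends on whether false cases replace true ones or, as extra codes would, add to them.

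**Conclusion.** The contradictions are in the text and should be corrected before extraction. Two bear on AMI: the unmarked event subset and one Read code. One bears on thromboembolism: two ICD-9-CM codes. One bears on the comparator: a single product line. One bears on fracture, and so on an RMM outcome.

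The expected effect on the safety endpoints is some dilution of the odds ratio towards 1 and inflated absolute rates. The dilution assumes that the wrongly counted cases have no association with SR; if SR also affected angina, it would be smaller. The documents do not allow its size to be estimated, and no power loss should be quoted. They also do not settle whether the Ankle row or the footnote is intended. Given the lists' provisional status, this is a low-cost correction and not a defect that invalidates the plan.

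**What to change.** 1. Issue a separate AMI event list without angina and other ischaemic heart disease codes, and keep the combined table for the contraindication. Retain the 411 codes as an HSD-only exception, with a sensitivity analysis that leaves them out.
2. Mark Read G32.. history-only.
3. Mark V12.51 and V12.55 history-only.
4. Remove the infusion concentrate from 14.3.1, and restrict M05BA06 to oral products where product data allow.
5. Reconcile the Ankle row, and any cervical-spine codes in the Spine row, with the footnote. State one fracture definition and align section 9.3.4 with it, including its appendix reference.

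The cost is a set of table edits before extraction and one added sensitivity analysis. The downside is somewhat fewer coded cases.
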